Institutional Review Board Intervention/Interaction Detailed Protocol

Principal Investigator: [name], DPhil

Project Title: TEAMS-BP (The Enhancement of social networks to Augment Management of Stroke-Blood Pressure): A Randomized Control Trial

Version Date: Version 17: March 27, 2024

1. Background and Significance

After ischemic stroke, blood pressure reduction is the most effective intervention to prevent recurrent stroke. Class I evidence suggests that the ideal blood pressure should be $< 130/80$.¹ However, maintaining this goal in real-world settings is challenging: one study suggested that only 42% achieved goal blood pressure at 1 year after stroke.²

Focus on the individual is common in the clinic and in research studies. Clinicians and researchers treat the patient as a solitary figure and the de facto unit of analysis. However, this is inconsistent with human nature.³ Social network theory proposes that every patient is embedded in a social network of interpersonal connections that influence health outcomes.⁴ Patients obtain information, social support, and behavioral cues through interpersonal contacts. In fact, there is a deep interdependence of social actors. Individual action is embedded in, and therefore continually affected by, preexisting ties between specific actors.⁵ Built on trust and reciprocity, these social networks are conduits of health resources and behavioral patterns, particularly in diet, exercise, and other lifestyle habits.⁴ Therefore, considering and leveraging social networks may be key strategy for addressing multi-dimensional behaviors. Indeed, ignoring them may be a key reason that behavioral interventions fail.⁶

The patient's personal social network is defined as the family, friends, and acquaintances who are interconnected in a unique web of ties that may be quantified as a graph. The study team has created a REDCap-based instrument to measure patients' personal social networks for clinical research. [name] and his colleagues have demonstrated that social networks are associated with outcomes in all phases of stroke care, including incident stroke,⁷ rapid arrival to the hospital,⁸ and recovery.⁹

Social networks could be leveraged to address hypertension control among post-stroke survivors for at least two reasons: 1) social networks influence and regulate the adoption of diet patterns, physical activity, and medication adherence, all of which are important to blood pressure management; 2) social network interventions relying on social support and social network education have been successful in blood pressure control in primary care settings.¹⁰

2. Specific Aims and Objectives

This proposed pilot project aims to leverage social networks to improve hypertension control for patients who have had an ischemic stroke. The study team hypothesizes that leveraging an individual's social network to monitor and treat blood pressure will be more effective than a standard intervention to control post-stroke blood pressure. This study has the following Specific Aims:

Aim 1: To determine the effects of a social network intervention versus individual hypertension counseling on blood pressure control for patients discharged after ischemic stroke. In a pilot study, the study team will randomize 60 patients with ischemic stroke to 1) individual teaching, and 2) a social network intervention. The primary outcome will be the absolute reduction in systolic blood pressure at 3 months.

Aim 2: To determine the shortest questionnaire that maximizes network information important for the intervention. We will test whether a subset of our social network questionnaire is sufficient for information used in the network intervention. For the same participant, we will compare intervention-relevant network metrics (network size, proportion of network members who have hypertension) derived from the short version versus full version.

[figure not shown]
Aim 3: To understand the acceptability, adoptability, and mechanisms of the social network intervention. The study will explicitly evaluate implementation of the intervention by collecting and evaluating quantitative and qualitative data directly from patients and their networks.

3. General Description of Study Design

The study will enroll 60 patients hospitalized at Brigham and Women's Hospital, Massachusetts General Hospital and Spaulding Rehabilitation Hospital with a symptomatic and imaging-confirmed ischemic stroke and hypertension. During the index stroke admission, all enrolled patients' networks will be mapped using the validated PERSNET instrument.¹¹ Participants will then be stratified according to network size (<5 vs 5 or more) and location of hospitalization (MGH or BWH). Network size is the most potent network metric related to stroke recovery.⁹ Patients in both arms will be administered blood pressure medications as needed during the hospitalization. Patients will then be randomized to receive individual hypertension counseling (control) or the social network intervention. In the individual hypertension counseling arm, patient networks will not be acted upon. The index patient will meet via Zoom three times over the course of 3 months with a clinical research nurse for blood pressure education. In the social network arm, the results of the PERSNET instrument will be used to identify the most influential network members based on their network position, driving distance from the patient, speaking frequency, and whether they have high blood pressure. Network members will then be contacted and consented for participation in the study. The index patient and consented network members will meet via Zoom for three visits over 3 months with a clinical research nurse for blood pressure education and teamwork coaching. The primary outcome of the study will be the absolute reduction in systolic blood pressure at 3 months follow-up.

3.1 Study Schema:

Screen potential participants hospitalized at MGB by inclusion and exclusion criteria Total N: 60 patients

4. Subject Selection

4.1 INCLUSION/EXCLUSION CRITERIA:

4.1a Patient subjects

The study team will enroll 60 patients hospitalized at Brigham and Women's Hospital, Massachusetts General Hospital and Spaulding Rehabilitation Hospital with a symptomatic and imaging-confirmed ischemic stroke and hypertension.

Inclusion Criteria:

1. Acute ischemic stroke defined clinically with support from imaging if necessary
2. 21 years of age or older
3. History of hypertension or has been newly prescribed blood pressure medications during index admission
4. Within 14 days after stroke

Exclusion Criteria:

1. NIHSS > 21
2. Significant aphasia (Score>1 on the language section of the NIHSS)
3. Medical conditions for which death is likely within 6 months
4. Does not have capacity to consent for the project or participate in survey interview
5. Diagnosis of dementia
6. Patient has no phone or incapable of using text messages
7. Patient has opted out of participating in research noted within MGB Epic EHR system
8. Patient is on enhanced respiratory, airborne or contact plus precautions

4.1b Network subjects:

Inclusion Criteria:

Those people 18 years of age or older identified by patient-subjects randomized to the intervention (social network) arm during completion of the validated PERSNET instrument will be included.

Exclusion Criteria:

1. Participants who do not meet the defined inclusion criteria
2. Participant has no phone or are incapable of using text messages
3. Does not agree to participate

4.1c Exclusion of non-English speaking participants

We plan to exclude patient- and network-subjects who do not speak basic English, as the counseling component of the pilot intervention program and study-related text messages will be in English and the program does not have the ability to translate any non-English inputs. We plan to expand the language ability of the program, pending the success of this pilot program.

4.2 RECRUITMENT PROCEDURES:

4.2a Patient subjects

Similar to IRB approved study ([name], 2020P003739), the Research Assistants (RA) or other study staff will perform daily EHR screening of Brigham and Women's Hospital, Massachusetts General Hospital and Spaulding Rehabilitation Hospital inpatient admissions based on the study's inclusion and exclusion criteria listed above. If an inpatient meets criteria, study staff will inform the primary neurologist and nursing staff of a potential patient participant on their service and request their approval for the patient to be contacted for research purposes. Study staff will then request the patient's nurse to introduce the study to the patient and obtain the patient's permission to be contacted by study staff during their inpatient stay. Once permission has been obtained by both the nursing staff and patient, the study staff will approach the patient.

The RA/study staff will meet with the patient at bedside, explain the study to the patient, and ask their permission to make inquiries about their social network. Specifically, this study will recruit patients of all gender identities, as well as patients of all racial and ethnic backgrounds if they meet these criteria. Patients will not be excluded or differentially selected for the study based on race/ethnicity or gender. Women and minorities are well represented at MGB and in the eligible study populations.

4.2b Network subjects

A list of each consenting patient's most close-knit network members will be obtained during the baseline questionnaire completion (validated PERSNET instrument) and documented within REDCap. The most influential network members will be ranked based on their network position, driving distance from the patient, speaking frequency, and whether they have high blood pressure. Potential network members will be contacted initially by the patient and study team member to introduce the study to them. This will be done via phone call during the index patient's enrollment visit, in which the index patient will initiate the conversation and the study staff will follow a script for recruitment (see *"Network member phone recruitment script" attachment*). If study staff are unable to get in touch with network members on first outreach, they will follow up with two additional phone calls on day 3 and day 10.

If the network member is interested in participation, they will be given the option to receive additional information and the study fact sheet via text message or email. The preferred method of outreach will be documented within REDCap, along with the appropriate email or phone number for contact.

- Network members who prefer **email outreach** will be read the following MGB-required warning language regarding unsecure email by study staff: *"The Mass General Brigham standard is to send email securely. This requires you to initially set up and activate an account with a password. You can then use the password to access secure emails sent to you from Mass General Brigham. If you prefer, we can send you "unencrypted" email that is not secure and could result in the unauthorized use or disclosure of your information. If you want to receive communications by unencrypted email despite these risks, Mass General Brigham will not be held responsible. Your preference to receive unencrypted email will apply to emails sent from this research group/study only."* The study staff will then obtain verbal permission to send unencrypted email and document within REDCap prior to sending any unsecure email.
- Network members who prefer **SMS message** outreach will be read the following warning language by study staff: *"SMS texting is not a secure form of communication. Message and data rates may apply."* The study staff will then obtain verbal permission to send SMS texting and document within REDCap prior to sending any SMS outreach.

- Network members will indicate their preference for how they receive a copy of their signed consent form during the consent process. Participants will be able to choose to receive the consent through email or mail and provide the address to send the consent form to.

Network members will then be sent a text message or email with a link to an MGB-approved secure REDCap study fact sheet. If network members agree to participate upon review of the Fact Sheet, they will click “I agree” within REDCap. In line with the Tier II texting requirements articulated in the MGB Texting Patients and Research Subjects Guidelines, the study team will also specifically obtain consent from the patient and network members to communicate with them via texts that may contain some limited PHI. As required by these guidelines, patient and network participants will both receive a welcome message (after the initial consent has been obtained) that includes a statement that texting is not secure and requests the patient to respond “yes” or “y” to indicate their preference to continue to receive texts. Once a patient enrolls by responding “Y”, a confirmation text will be sent that notifies them of the opt out process and discloses potential message and data charges the patient may incur (see “*Text message list*” attachment). If network members agree to participate over the phone but do not formally give their consent within REDCap, study staff will follow up with two additional messages, sent via the network member’s preferred form of communication, 3 and 10 days after the initial outreach (see “*Network Member Recruitment Texts*” attachment).

5. Subject Enrollment

The study staff will obtain informed, written consent from all patients, and all network members will agree to participate using an electronic consent process through REDCap. Before being enrolled in the study, all participants will be required to give their consent to participate in the study. The RA/study staff will review either the written informed consent document (patient-subjects) or the study fact sheet (network-subjects) with all participants and answer any questions that they may have before the subjects agree to participate. Subjects will not be able to participate in any portion of the study before giving their written informed (patient) or electronic (network) consent.

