All network members will then be asked to leave the Zoom meeting, except for the primary caregiver (if applicable). The patient will collect a final blood pressure measurement under direct supervision of the study nurse, complete the PROMIS physical function scale, and remap their network with the PERSNET instrument to assess any changes that may have occurred as a result of the study. The primary caregiver network member will be asked to complete the caregiver burden scale which will be sent to them via a link in the Zoom chat or via text message.

Outcomes

The primary outcome of the study will be absolute reduction in systolic blood pressure at 3 months. Secondary outcomes will be attainment of a post-stroke hypertension treatment goal and patient-reported physical function. Feasibility measures will also be assessed throughout the intervention. End line caregiver burden will be measured in the social network arm compared to historical control data.

The intervention process evaluation conducted using semi-structured qualitative interviewing during the final session (Social Networks arm) will be analyzed using qualitative software to identify themes using a grounded theory approach. Once the data are analyzed, the investigators will review the findings to consolidate observations into a common set of themes.

Finally, a shortened version of the validated PERSNET utilizing only a subset of the initial questionnaire will be tested for predictive accuracy against the results of the full validated PERSNET scale.

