9.3 Statistical analysis

The primary outcome will be absolute reduction in systolic blood pressure at 3 months. Secondary outcomes will be attainment of a post-stroke hypertension treatment goal of <130/80 and patient-reported physical function (based on the NIH PROMIS physical function sub-scale). These outcomes will be evaluated, for intervention and control patients, on a 10-minute Zoom exit interview with direct observation on video by the study nurse.

Analysis will be conducted using intention-to-treat principles. Evaluation of the primary outcome and physical function secondary outcome will be completed using linear controlling for any differences in baseline variables despite randomization. Logistic regression will be used for attainment of post-stroke hypertension treatment goal of <130/80 controlling for any differences in baseline variables.

For Aim 2, we will assess how a subset of questions in PERSNET predict the set of network members who were engaged in the intervention. We will calculate positive predictive value of the subset questions versus full network survey questions.

10. Monitoring and Quality Assurance

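### Aim 2 is defined in two different ways, and neither measure tests whether a short PERSNET form would pick the same team as the full form

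*Combined protocol and SAP*

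**What the plan says.** Aim 2 in Section 2 is worded as a search: "To determine the shortest questionnaire that maximizes network information important for the intervention". The next sentence describes a test: "We will test whether a subset of our social network questionnaire is sufficient for information used in the network intervention". The comparison is within participant, short form against full, on "intervention-relevant network metrics (network size, proportion of network members who have hypertension".

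Section 9.3 gives a different target and statistic: "we will assess how a subset of questions in PERSNET predict the set of network members who were engaged in the intervention", followed by "We will calculate positive predictive value of the subset questions versus full network survey questions". The Outcomes text under Section 6.4 says only that a shortened version "will be tested for predictive accuracy against the results of the full validated PERSNET scale".

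Sections 3, 4.2b and 5.2 agree on how the intervention ranks network members: "based on their network position, driving distance from the patient, speaking frequency, and whether they have high blood pressure".

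Every patient completes PERSNET at baseline, before randomization (Section 6.1). Section 6.6 plans 60 patients, 30 per arm. Members are invited only in the social network arm. They must be adults with a phone who can text and who agree to take part (Section 4.1b). The patient may ask for more members to join at any time in the 12 weeks (Section 5.2).

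The text available does not list the short-form items, say whether they are fixed beforehand or chosen from trial data, set a level that counts as sufficient, or describe any validation step. A figure beside Aim 2 is not shown and may hold some of this.

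**The concern.** The product of Aim 2 is a shorter instrument for later use, and its job is to choose the team. The relevant question is whether the short form, given to the same patient, would lead staff to the same people.

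Section 2 asks whether two network summaries agree, and one of them (network size) is a stratification factor and not a ranking input. Section 9.3 asks whether flagged members ended up taking part, which depends on events outside the questionnaire. A form could pass either test and still choose a different team. It could also do badly on the second because invited people declined.

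A further risk applies if several candidate subsets are compared on these patients and the best is reported on the same patients: its accuracy will tend to be overstated.

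**Working it through.** The documents give no sample size, precision target or threshold for Aim 2, so there is no Aim 2 figure to reproduce. The check sets each measure against the ranking rule, then sizes the possible optimism.

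**1. Section 2 metrics against the ranking inputs**

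| Ranking input (Sections 3, 4.2b, 5.2) | In the Section 2 metrics? |
|---|---|
| Network position | No |
| Driving distance | No |
| Speaking frequency | No |
| High blood pressure | Only as a network proportion |

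Coverage is 1 of 4. The short form is cut from the same answers. A form with the name list and the hypertension item therefore gives the same network size and the same proportion as the full form in every patient, by construction. It holds no distance or speaking-frequency data, and no tie data from which to compute position.

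Illustration of the loss. Assumptions, none from the documents: four independent, equally weighted inputs; networks of 5 to 10; 40% hypertensive; three members picked; ties broken at random.
- Overlap with the full-form top three, by simulation: 0.60.
- Overlap by chance, the mean of 3/n for n = 5 to 10: 3 × (1/5 + 1/6 + 1/7 + 1/8 + 1/9 + 1/10) / 6 = 0.42.

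So this form agrees 100% on both Section 2 metrics and about 60% on the team.

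**2. The Section 9.3 measure**

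- *Missed members.* Suppose four members are engaged and the short form flags one of them and nobody else. PPV = 1/1 = 100%; sensitivity = 1/4 = 25%. PPV alone rewards a form that flags few people.
- *Non-form influences.* Suppose the short and full forms pick the same three people and one declines. PPV = 2/3 = 67%, although the forms agree on 3/3.
- *Patients.* Only the 30 intervention patients can have engaged members. Assuming three flagged per patient (90 members) and PPV 0.70, the 95% half-width is 1.96 × √(0.70 × 0.30 / 90) = 9.5 points. With all 60 patients (180 members) it is 1.96 × √(0.21 / 180) = 6.7 points.
- *Clustering.* Members are nested within patients, so the standard error grows by √(1 + (m − 1) × ICC). For m = 3 and ICC 0.1 this is √1.2 = 1.1; for m = 8 and ICC 0.3 it is √3.1 = 1.8.

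**3. Optimism, if the subset is chosen on these patients**

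Assumptions: K candidate subsets with the same true PPV of 0.70, 90 flagged members, correlation between subsets 0 to 0.8. The best subset is picked and scored on the same data.

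| K | Apparent minus true PPV (points) |
|---|---|
| 1 (fixed in advance) | about 0 |
| 5 | 3.6 to 5.4 |
| 20 | 5.7 to 8.8 |
| 100 | 7.4 to 11.7 |

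A second set of assumptions (true accuracy 80%, three members per patient, within-patient correlation 0.2, between-subset correlation 0.5 to 0.8, K = 10 to 200) gives 3.4 to 9.7 points with 30 patients and 2.4 to 6.8 with 60. Varying the first set over 60 to 150 flagged members and true PPV 0.6 to 0.8 gives 2.3 to 15.4 points for K = 5 to 100. For scale, eight candidate items allow 2⁸ − 1 = 255 subsets.

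**The case against.** The strongest reply is that Section 9.3 is where the analysis is specified, and its target lies downstream of all four ranking inputs. A names-plus-hypertension form would not pass Section 9.3 merely by matching the Section 2 metrics. This stands: the coverage gap belongs to Section 2 and not to Aim 2 as a whole. It does not rescue Section 9.3, whose limits are separate. The Section 9.3 sentence could also mean that the short-form and full-form PPVs are contrasted, in which case consent would affect both. Missed members and the restriction to one arm would remain.

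A reader might infer that the plan searches for the best subset and scores it on the same patients, so that the short form is bound to look better than it is. The documents do not support that. Section 2 speaks of a subset and Section 6.4 of a shortened version, and both fit one form fixed in advance, where selection optimism is about zero. Comparing two forms within a participant is not a flaw in itself. Narrow metrics leave sufficiency untested; they do not inflate the agreement that is measured. Direction is also open under Section 9.3: refusals can lower PPV, while choosing engaged members from full PERSNET answers that contain the short-form items favours agreement.

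It is also fair that the magnitudes rest on inputs absent from the documents, and that giving every candidate the same true accuracy favours a large selection effect. Finally, this is a secondary aim of a pilot; the blood pressure comparison is untouched.

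**Conclusion.** The point holds in this form. Sections 2 and 9.3 define Aim 2 differently, and neither measure shows whether a short form would select the same team. That conclusion follows from the text and needs no numerical assumption: coverage of one ranking input in four in Section 2; and in Section 9.3 a PPV that ignores missed members, can be computed in 30 of 60 patients, and depends on consent, phone access and later additions.

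The sizes are illustrative. The 60% against 42% overlap depends on the assumed weights, network sizes and hypertension share. Optimism is conditional on data-driven selection: roughly 2 to 12 points in the base cases, up to about 15 over the wider range, and about zero for a single form fixed beforehand. The documents do not settle which case applies. The change is worth making because the aim's output is a tool for reuse and the remedy costs little.

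**What to change.** 1. Reconcile Sections 2 and 9.3 on one Aim 2 measure: for each patient, agreement between the member list ranked from the short form and the list ranked from the full form. Report overlap, or sensitivity together with PPV. Compute it in all 60 patients, since baseline PERSNET is taken in both arms and the control-arm list can be derived without being acted on. Write the ranking rule down so that both lists can be generated; the documents give its inputs but no weights or list length. Take confidence intervals from a bootstrap that resamples patients. State in advance what level of agreement counts as sufficient. Network size, proportion hypertensive and engagement can stay as descriptive results.

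2. Either list the short-form items before the data are analysed or, if they are chosen on trial data, report performance from patient-level cross-validation or bootstrap with the selection repeated in each resample.

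Cost: revised wording in Sections 2 and 9.3 and a few lines of code, with no new data or patient burden. The downside is slightly more analysis work, and the reported short-form accuracy may be a few points lower.
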